3 STUDY DESIGN

3.1 General outline

This is an open-label, single-armed, multi-center study to evaluate clinical performance, tolerability, and safety of Gedea Pessary in 24 adult women with VVC. Patients seeking treatment can be screened for study participation. Included patients will have gynecological examination, including collection of CVVS data, vaginal samples taken, and will receive the

Protocol Version 3.0, 24Oct2018

[figure not shown]
LINK Medical Research | Protocol template

Version 2.0 | Effective date 17Apr2018

investigational product to be self-administered at Day(s) 0, 2, 4, and 6. Patients will again be examined after 7 days and CVVS data will be collected. Prolonged treatment at Day(s) 7, 9, 11, and 13 will be given to patients not cured at Day 7; including re-examination at Day 14. Patients will be followed up by telephone up to 29 days after last treatment administration. Vaginal samples will be used for confirming diagnosis and microbiome analyzes. Patient questionnaires will be used for assessing VVC symptoms, usability, and AEs.

Figure 1 Study Flow Chart

Patients not receiving prolonged treatment

VVS = Vulvovaginal Symptoms, VS = Vaginal Swab, CVVS = Composite Vulvovaginal Signs and Symptoms

Patients not receiving prolonged treatment applies to patients cured at Day 7. If not cured, the flow chart *patients receiving prolonged treatment* applies. Patients will here receive fluconazole if not cured at Day 14. Adverse events will be assessed throughout the study

Protocol Version 3.0, 24Oct2018

LINK Medical Research | Protocol template

Version 2.0 | Effective date 17Apr2018

3.2 Rationale for Study Design

As described in [Section 1.1](#), VVC is a major clinical concern, and new effective interventions not associated with antibiotic resistance and major drug interactions would be valuable additions to the current treatment arsenal. This study aims to investigate the clinical performance and safety of the Gedea Pessary containing GDL and NaG in treating VVC.

Previous *in vitro* data show that GDL inhibits both bacterial and fungal biofilm formation, and transforms *Candida* to a non-adhesive form (see [Section 1.2](#)). In addition, a device comparable to Gedea Pessary with regards to its pH-lowering and biofilm-inhibiting properties, used for treating BV, have shown high cure rates.⁴⁴ Data also indicate that GDL is tolerable and does not pose any special risk to humans ([Section 1.3.1](#)).

Based on this, it may be argued that a trial involving patients is justified due to the widespread clinical problem of VVC and the issues involving current therapies (see [Section 1.1](#)). Further, due to that the pessary has not been evaluated clinically prior to this study and the lack of proper comparators, a single-arm design has been chosen, allowing evaluation of clinical performance on a smaller number of patients. Due to the open-label design, risks for introducing assessor bias have been minimized by the use of well-defined and documented scales, as well as objective laboratory assessments.

The dose of 300 mg GDL and 376.5 mg NaG administered 2 days apart on Day(s) 0, 2, 4, and 6^a was chosen based on pre-clinical data, specifically an *in vitro* dissolution test of the Gedea Pessary using a vaginal fluidic model (see IB). Measurements of pH in the *in vitro* dissolution test showed a pH-decrease duration of approximately 45 hours.

3.2.1 Risks and Benefits

The investigational device, Gedea Pessary has been evaluated in accordance with ISO 10993 (Biological Evaluation of Medical Devices). The evaluation included: cytotoxicity testing (Direct cell contact test, ISO 10993-5); *in vivo* irritation (Vaginal acute irritation; ISO 10993-10); and sensitization (local lymph node assay, ISO 10993-10). The *in vitro* cytotoxicity test, classified the test item as slight to moderate cytotoxic (scale 1–2 on a 3-grade scale); the *in vivo* irritation test as well as the *in vivo* sensitization test showed no signs of irritation, necrosis or sensitization after treatment with Gedea Pessary.

The vaginal pessary may, in similarity with other vaginally administered products, cause temporary minor discomfort at insertion. The vaginal sampling procedures are similar to sampling procedures used in clinical practice are unlikely to cause any major inconvenience to patients. In the Laccure pessary study,⁴⁴ there were no SAEs and vaginal itching was the most common AE.

There is a risk that patients will have no clinical benefit from the investigational device. This may cause patients to experience symptoms including vaginal itching, burning or soreness, pain during sexual intercourse, pain or discomfort when urinating, or abnormal vaginal discharge longer than necessary.^{1,45} However, fluconazole will be offered on Day 14 if any symptoms should still be present, thus avoiding any risk associated with long-term untreated VVC.

^a And on Day(s) 7, 9, 11, and 13 if receiving prolonged treatment

Protocol Version 3.0, 24Oct2018

LINK Medical Research | Protocol template

Version 2.0 | Effective date 17Apr2018

Subjects included in the study must refrain from using other intravaginal products, thus mitigating the risk of interactions with concomitant vaginally-administered products. The investigational device acts locally on the vaginal mucosa and most likely will most likely not affect any concomitant systemic treatment.

Taken together, as the anticipated levels of discomfort are transient and mild, and that risks associated with VVC are avoidable, the use of the investigational product appears to offer clinical benefits at a reasonable risk level.

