3.5.5 Day 7 (+2 Days); Follow-up Visit

Patients will visit the clinic on Day 7 to have gynecological examination performed. The Investigator or an authorized designee will assess the presence of vulvovaginal signs (erythema, edema, or excoriation) and symptoms (itching, burning, or irritation) and score each sign and symptom.

Vaginal samples will be examined by microscope to reveal yeast forms (hyphae or pseudohyphae) or budding yeast and secretion samples collected by swab to be used for sequencing analysis of the vaginal microbiome. Vaginal pH will also be assessed.

If VVC symptoms are still present, patients will have prolonged treatment and receive additional doses of investigational product to be administered at home on Day(s) 7, 9, 11, and 13.

In addition, patients will be asked questions from the patient questionnaire to assess: usability; concomitant medications; and AEs, if any.

Procedures performed:

- Gynecological examination by Investigator or authorized designee evaluating signs (erythema, edema, or excoriation) and symptoms (itching, burning, or irritation of VVC according to the scoring scale
- Fungal KOH microscope assessment
- Vaginal swab for sequencing
- Vaginal pH
- Recording of:
 - concomitant medications,
 - adverse events, and
 - usability
- Treatment dispensing and self-administration by patients if receiving prolonged treatment

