5 TREATMENTS

5.1 Investigational Product

The investigational product, Gedea Pessary (commercial name *p*Hyph), is a GDL-and-NaG containing pessary to be administered vaginally with a CE-marked vaginal tablet applicator (Schägner GmbH, Steinmauern, Germany). The device is intended to treat vaginal Candida infections, see [Figure 2](#) and [Figure 3](#) for product image and applicator label. Gedea Pessary is a Class IIa medical device according to MDD 93/42/EEC (the Swedish regulation SFS 1993:584 and LVFS 2003:11).

NOTE: The terms investigational product, Gedea Pessary, investigational device, pessary, and vaginal pessary are used interchangeably in the CIP

Gedea Pessary is a white, convex, bullet-shaped tablet, approximately 2 cm in length, contract-manufactured by Galenica AB (Malmö, Sweden). The pessary is slow-release formulated, administering 300 mg GDL and 367.5 mg NaG over 45 hours. Each patient will administer a total of 4 pessaries in the study or 8 if receiving prolonged treatment. The investigational products will be packed in blister packs containing 4 pessaries labeled with *Gedea Pessary* and batch number. Blisters will be packed together with 4 vaginal tablet applicators in a cardboard-box labeled with *Gedea Pessary, for investigational use only*, production date, and expiry date ([Figure 4](#)).

It is the responsibility of the Investigator to ensure that the investigational products are stored in their original packaging in a secure location with access only by authorized personnel, separate from other medications. The investigational product shall be stored at room temperature (15°C -25°C), protected from direct sunlight or freezing. The investigational products *must not* be used outside of the study. For further reference, refer to the IB.

Instructions for use will be distributed at the first visit, advising patients on how to use the product together with the applicator. Briefly, patients will be instructed to: wash their hands and vaginal area prior to use; place a tablet into the applicator and insert as far into the vagina

as is comfortable (without forcing), or until half of the applicator is inside; discard the applicator after use; not use tampons or other vaginal products while using this product.

[figure not shown]
Figure 2 Gedea Pessary and Applicator

Figure 3 Vaginal Tablet Applicator Label

Figure 4 Investigational Product Label

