## 7.8 Compliance

Patients will be asked about investigational product administration by telephone on Day 4 and at the site on Day 7, and also on Day(s) 11 (telephone) and 14 (site) if receiving prolonged treatment. No other measurements of treatment compliance will be made. These compliance data will be summarised for the full analysis set. The rate of compliance is defined as the actual amount of study treatment taken divided by the expected amount of study treatment to be taken. The expected amount is based on the planned duration of treatment (*i.e.* for prematurely withdrawn patients, the expected amount is computed as if the patient had not withdrawn). The expected amount is 4 doses for patients without prolonged treatment and 8 doses for patients with prolonged treatment.

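### The prolonged course starts one day after the Day 6 dose with no explanation, its fixed days do not fit the Day 7 (+2) visit, and the listed AE tables do not separate the two courses

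*Protocol*

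**What the plan says.** **Interval.** Protocol Section 3.2 says the product is "administered 2 days apart on Day(s) 0, 2, 4, and 6". It bases this on an in vitro dissolution test that "showed a pH-decrease duration of approximately 45 hours". The footnote marked on that sentence, printed under Section 3.2.1, reads "And on Day(s) 7, 9, 11, and 13 if receiving prolonged treatment". Section 5.1 separately describes the pessary as "administering 300 mg GDL and 367.5 mg NaG over 45 hours".

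**Prolonged course.** Section 3.1 states: "Prolonged treatment at Day(s) 7, 9, 11, and 13 will be given to patients not cured at Day 7". The visit that starts it is headed "3.5.5 Day 7 (+2 Days); Follow-up Visit". There, patients with remaining symptoms "receive additional doses of investigational product to be administered at home on Day(s) 7, 9, 11, and 13". For the Day 4 and Day 11 telephone contacts, the protocol keeps the dose on its nominal day even when the call is late. Section 3.5.5 has no matching rule for the Day 7 visit.

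**Analysis.** SAP 8.9 counts a patient as having prolonged treatment if she took product on any of Days 7, 9, 11 or 13. SAP 7.8 says: "The expected amount is 4 doses for patients without prolonged treatment and 8 doses for patients with prolonged treatment". SAP 7.10 runs all safety evaluations on the full analysis set (FAS). SAP 7.10.2 defines treatment-emergent events from the first dose and lists tables by system organ class, preferred term, severity and causality. None is by course. SAP 7.2.1 forms prolonged and non-prolonged subsets of the FAS, but the SAP assigns no AE table to them.

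**The concern.** The footnote hangs the prolonged days on a sentence about two-day spacing, yet the join between the courses is a single day, shorter than the duration quoted in support of the spacing. The reader cannot tell whether that is intended.

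The late-visit problem follows from the same fixed list. When the dispensing visit uses its window, the listed days cannot all be kept, and sites have no rule for what follows. SAP 8.9 then turns the list into a derived variable, so a patient who took a full second course could be classed as not having had one.

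Safety and tolerability is a co-primary endpoint, judged on AEs alone, for a product that Section 1.3.2 says has no previous clinical trials. Events arising when the second course begins are of particular interest, and the listed tables mix them with events from all patients at all times.

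**Working it through.** **1. Intervals.** Inputs: dosing Days 0, 2, 4, 6 (Section 3.2) and 7, 9, 11, 13 (footnote, Sections 3.1 and 3.5.5, Table 3); duration about 45 h (Sections 3.2 and 5.1).

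Gap = difference in days × 24 h. Nominal overlap = max(0, 45 − gap).

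| From – to | Gap (h) | Overlap (h) |
|---|---|---|
| 0–2, 2–4, 4–6 | 48 each | max(0, 45 − 48) = 0 |
| 6–7 | 24 | 45 − 24 = 21 |
| 7–9, 9–11, 11–13 | 48 each | 0 |

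The plan's two-day interval is reproduced in six of seven steps. It fails only at the join.

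**2. Late Day 7 visit.** These rows show what different readings of the text would produce. None is a proposed schedule. The shifted course assumes two-day spacing from the visit.

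| Visit on | Listed days still available | Whole course shifted | SAP 8.9 flag if shifted |
|---|---|---|---|
| Day 7 | 7, 9, 11, 13 | 7, 9, 11, 13 | met |
| Day 8 | 9, 11, 13 | 8, 10, 12, 14 | not met (0 of 4 on listed days) |
| Day 9 | 9, 11, 13 | 9, 11, 13, 15 | met (3 of 4 on listed days) |

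- A patient seen on Day 8 or 9 and held to the listed days can take at most 4 + 3 = 7 of the 8 expected doses: 7/8 = 87.5% compliance.
- A patient who doses on Day 8 and rejoins the list on Day 9 has a 48 h gap after Day 6, but then a 24 h gap with 21 h nominal overlap.
- A first second-course dose on Day 9 follows Day 6 by 72 h, with no overlap.
- The shifted Day 8 patient drops out of the numerator of the secondary endpoint on prolonged treatment. If the same flag also sets the expected amount in SAP 7.8, her compliance would be 8/4 = 200%.

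**3. Dilution in the AE tables.** Expected number with a second course = 24 × (1 − cure rate).

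- Cure 70% (the planning assumption): 24 × 0.30 = 7.2, about 7.
- Cure 40% (the null value): 24 × 0.60 = 14.4, about 14.

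Suppose an event occurs only in the second course, in a proportion q of patients who receive it. The documents give no q, so 10% and 20% are my assumptions. Percentage shown on the FAS = q × k / 24.

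| q | k = 7 | k = 14 |
|---|---|---|
| 10% | 0.10 × 7/24 = 2.9% | 0.10 × 14/24 = 5.8% |
| 20% | 0.20 × 7/24 = 5.8% | 0.20 × 14/24 = 11.7% |

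**The case against.** The strongest reply is that the documents agree on the days. Days 0, 2, 4, 6 and then 7, 9, 11, 13 recur throughout, each course is internally two days apart, and the total of eight doses matches. The two-day phrase stands before the first-course list, and the footnote only adds days. The 45-hour figure is approximate and in vitro. It can be read as saying how often to redose to maintain an effect, and nothing says pessaries must not overlap. All of that stands. A reader might infer that 45 hours sets a minimum interval that the schedule breaches, or that the overlap is unsafe. The documents support neither: they state no minimum, Section 3.2.1 reports no in vivo irritation or sensitization, and the Investigator's Brochure, cited for the dissolution work, is not available here. Nor do the synopsis or Section 5.1 argue for an interval; one lists days and the other gives a release duration. What survives is that the footnote ties the second course to the two-day sentence and no passage explains the one-day step.

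On the window, a reader might infer that a course ending on Day 15 outruns the final treatment visit. It does not: that visit is Day 14 (+2), so Day 15 is inside it, although off the listed dosing days. A Day 9 start also removes the Day 6 overlap, so the two problems do not fall on the same patient.

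On safety, a reader might infer that second-course events would be invisible. They would not. AEs are asked about at every contact, the co-primary safety evaluation includes data listings, SAP 7.1.3 defines days from first dose, and the Data Display Plan, which is not available, may hold further tables. With about 7 patients, listings can be read by eye. The supportable claim is dilution in the tables the SAP lists. Tables by prolonged and non-prolonged subset would still not separate the courses within a patient.

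**Conclusion.** The point holds as a minor one, in three parts: an unexplained one-day step between courses (nominally 24 h, about 21 h overlap); fixed dosing days that a Day 8 or Day 9 visit cannot satisfy, with a flag in SAP 8.9 that misses a course on Days 8, 10, 12 and 14; and listed AE tables that dilute second-course events.

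The 21 hours is nominal, since it rests on an approximate in vitro duration and calendar-day spacing with no stated clock time. The counts of about 7 and about 14 assume that all 24 patients reach Day 7 and that the second course goes to those not cured, as Section 3.1 says. Section 3.5.5 words the trigger as remaining symptoms, which could bring in more patients. The number of late visits cannot be predicted from the documents, so the number misclassified by SAP 8.9 may be zero. The Day 7 cure analysis is unaffected, because the prolonged course starts only after that assessment.

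**What to change.** 1. **Protocol.** Reconcile Section 3.2 and its footnote, Section 3.5.5, Table 3 and SAP 8.9 on two matters: whether the Day 6 to Day 7 interval is intended, and which dosing days apply after a Day 7 visit held on Day 8 or 9. The schedule is for the sponsor to decide.
2. **SAP 8.9.** Define prolonged treatment as receipt of any second-course dose, whatever the calendar day. Use the same flag for the subsets in SAP 7.2.1 and the expected amount in SAP 7.8.
3. **SAP 7.10.2.** Add one AE table by course of onset: before the first second-course dose, and from that dose onward. Use the FAS as denominator for the first column and prolonged-treatment patients for the second. State how an onset on the same day as that dose is assigned.

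The cost is a protocol clarification, a one-line change to a derivation, and one extra table; the SAP changes can be recorded in SAP 7.11. The second-course column will be small. The columns are also not a comparison: patients without a second course contribute their follow-up to Day 35 to the first column, prolonged patients contribute only about a week to it, and the second column contains only patients selected for the second course. A table note should say so.

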3.3 Recruitment

Patients will be recruited at study sites' gynecological clinics. Post-menarchal, pre-menopausal females 18 years or older seeking for VVC symptoms may be informed verbally and in writing about the study and screened following signed informed consent. Patients may also be pre-informed about the study by the use of advertisement through social media; these patients will directly book appointments with the clinic. The recruitment of patients will start only after the approval of the clinical investigation plan (CIP) by the regulatory authorities (RA) and the independent ethics committee (IEC). No study procedures will be performed unless the patient has provided written informed consent to study participation. See also [Section 4.1](#).

3.4 Schedule of Assessments and Procedures

Table 2 Schedule of Assessments and Procedures, No Prolonged Treatment

Evaluations	Day 0	Day 2	Day 4 (+2 days)	Day 6	Day 7 (+2 days)	Day 14 (±2 days)	Day 35 (±2 days)
	Screening		Follow-up		Follow-up	Follow-up	Follow-up
	Visit 1		Visit 2		Visit 3	Visit 4	Visit 5
	Visit	Telephone		Visit	Telephone	Telephone	
Informed Consent	X						
Eligibility Criteria	X						
Pregnancy Test (Urinary)	X						
Medical History	X						
Concomitant Medications	X		X		X	X	X
Gynecological Examination including vulvovaginal signs	X				X		
Vulvovaginal Symptoms	X		X		X	X	X
Recurrence						X	X
Fungal Microscope Assessment	X				X		
Vaginal Swab for Culture	X						
Vaginal Swab for Sequencing*	X				X		X
Treatment	X	X	X	X			
Vaginal pH	X				X		
Usability					X		
Adverse Events	X		X		X	X	X
Product Accountability					X		

* Self-swab at Day 35.

Protocol Version 3.0, 24Oct2018

LINK Medical Research | Protocol template

Version 2.0 | Effective date 17Apr2018

Table 3 Schedule of Assessments and Procedures, Prolonged Treatment

Evaluations	Day 0	Day 2	Day 4 (+2 days)	Day 6	Day 7 (+2 days)	Day 9	Day 11 (+2 days)	Day 13	Day 14 (+2 days)	Day 21 (±2 days)	Day 42 (±2 days)
	Screening		Follow-up		Follow-up		Follow-up		Follow-up	Follow-up	Follow-up
	Visit 1	Visit 2	Visit 3	Visit 4	Visit 5	Visit 6	Visit 7				
	Visit	Telephone	Visit	Telephone	Visit	Telephone	Telephone	Visit	Telephone	Telephone	Telephone
Informed Consent	X										
Eligibility Criteria	X										
Pregnancy Test (Urinary)	X										
Medical History	X										
Concomitant Medications	X	X	X	X	X	X	X	X	X	X	X
Gynecological Examination including vulvovaginal signs	X			X					X		
Vulvovaginal Symptoms	X	X	X	X	X	X	X	X	X	X	X
Recurrence										X	X
Fungal Microscope Assessment	X			X					X		
Vaginal Swab for Culture	X										
Vaginal Swab for Sequencing*	X			X					X		X
Treatment	X	X	X	X	X	X	X	X			
Vaginal pH	X			X							
Usability				X					X		
Adverse Events	X		X	X	X	X	X	X	X	X	X
Product Accountability				X					X		

* Self-swab at Day 42.

3.5 Study Visits and Procedures

3.5.1 Day 0; Screening and Enrollment

Patients seeking treatment for symptoms relating to VVC may be informed about the study and, if agreeing to participate, sign the informed consent form (ICF). After enrollment, patients will have gynecological examinations performed, where the Investigator or an authorized designee will assess the presence of vulvovaginal signs (erythema, edema, or excoriation) and ask about symptoms (itching, burning, or irritation) and score each sign and symptom, as described in [Section 6.1](#).

Vaginal samples will be examined by microscope to reveal yeast forms (hyphae or pseudohyphae) or budding yeast. Two (2) vaginal secretion samples will also be collected by swab. One (1) of the samples will be cultured to verify presence of *Candida* and 1 sample will be used for sequencing analysis of the vaginal microbiome prior to treatment ([Section 7.2](#)). If the Investigator assesses that the patient has VVC, based on examination and the KOH test, the patient will receive the investigational product to be self-inserted vaginally at home on Day 0. Additional doses will also be dispensed to be administered by patients on Day(s) 2, 4, and 6. In addition, the Investigator will measure vaginal pH.

Procedures performed:

- Informed consent
- Eligibility criteria
- Pregnancy test (urinary)
- Recording of:
 - medical history,
 - concomitant medication, and
 - adverse events
- Gynecological examination by Investigator or authorized designee evaluating signs (erythema, edema, or excoriation) and symptoms (itching, burning, or irritation) of VVC according to the scoring scale
- Fungal KOH microscope assessment
- Vaginal swab for:
 - culture, and
 - sequencing
- Vaginal pH
- Treatment dispensing and self-administration by patients

3.5.2 Day 2; Treatment Administration

Procedures performed:

- Treatment self-administration by patients

3.5.3 Day 4 (+2 Days); Follow-up Telephone Contact

On Day 4, patients will self-administer the investigational product and will be contacted by telephone by the Clinical Trial Unit. Telephone contact up to Day 6 will be allowed if Day 4 falls on a weekend. The treatment should nevertheless be self-administered on Day 4. Patients

will be asked questions from the patient questionnaire about: VVC symptoms (itching, burning, or irritation); concomitant medications; and AEs, if any.

Procedures performed:

- Treatment self-administration by patients
- Symptoms of VVC (itching, burning, or irritation) evaluated by patients according to the scoring scale
- Recording of:
 - concomitant medications, and
 - adverse events

